5.2.2. Analyses for Continuous Efficacy Data

The descriptive statistics will be used to summarize continuous data. The continuous data and change from baseline will be summarized descriptively by visit and dose group, regimen group and the subgroup of subjects who are initially assigned to tofacitinib 5 mg BID and later are retreated with tofacitinib 10 mg BID.

For continuous efficacy endpoints based on total Mayo score evaluated for primary objective at Month 6, the change from baseline will be analyzed using an analysis of covariance (ANCOVA) model with dose group, the endoscopic subscore at baseline (0 versus 1) as factors and baseline score as a covariate. Otherwise, for continuous efficacy endpoints, the change from baseline will be analyzed using linear mixed effects model with baseline value, dose group or regimen group, the endoscopic subscore at baseline (0 versus 1), visit, and dose group or regimen group by visit interaction all as fixed effects, and subject as a random effect. The adjusted estimations and associated 95% CI for the overall difference between the two dose groups or two regimen groups will be computed at each visit.

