4.1. Inclusion Criteria

Subjects must meet all of the following inclusion criteria to be eligible for enrollment into the study:

1. Subjects currently enrolled in Study A3921139 who have received tofacitinib 10 mg BID for a minimum of 2 consecutive years in Study A3921139 prior to and including baseline of Study A3921288.
2. Subjects who are in stable remission on tofacitinib 10 mg BID for the 6 month period in Study A3921139 up to and including baseline of Study A3921288, defined as meeting all of the following criteria:
 - a. A partial Mayo score ≤ 2 , with no individual subscore > 1 and a rectal bleeding subscore of 0 at each study visit where data is available during the 6 month period in Study A3921139 prior to and including baseline of Study A3921288;
 - b. **AND** at least one assessment of remission based on Mayo score;
 - If an endoscopy was not completed ≤ 6 months prior to baseline of Study A3921288, then an endoscopy performed in Study A3921139 with an endoscopic subscore of 0 or 1, will be required prior to randomization into Study A3921288.
 - All available assessments based on Mayo score during this period must show remission.
 - c. **AND** subjects must not be receiving any corticosteroid therapy for their UC for at least 4-weeks prior to baseline.

3. Female subjects of childbearing potential must agree to use a highly effective method of contraception throughout the study and for at least 28 days after the last dose of assigned treatment. Subjects in Canada who are women of childbearing potential and sexually active must use two contraceptive methods at the same time: one highly effective contraceptive method and one additional effective contraceptive method (see [Section 4.4.4](#)).
4. Female subjects of childbearing potential must have a negative urine pregnancy test prior to randomization.
5. Subjects who are willing and able to comply with scheduled visits, treatment plan, laboratory tests, bowel movement diary calls, and other study procedures.
6. Evidence of a personally signed and dated informed consent document indicating that the subject has been informed of all pertinent aspects of the study.

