9.2.3. Secondary Analysis

Dose comparison between tofacitinib 5 mg BID and 10 mg BID

For the primary objective, the treatment difference for the binary secondary efficacy endpoints will also be estimated based on the FAS, using the same approach as described above for the primary endpoint. For continuous endpoints, the change from baseline will be analyzed using linear mixed-effects model with baseline value, dose group, the endoscopic

subscore at baseline (0 versus 1), visit, and dose group by visit interaction all as fixed effects, and subject as a random effect. The adjusted estimations and associated 95% CI for the overall difference between the two dose groups will be computed. Kaplan-Meier estimates at the scheduled visits will be computed for time to event endpoint. The log-rank test stratified by endoscopic subscore at baseline (0 versus 1) will also be performed for the comparison between dose groups.

If a subject has a dose escalation back to tofacitinib 10 mg BID, then

- For binary efficacy endpoints, the subject will be considered as a non-responder for any visit after the dose escalation visit.
- For continuous efficacy endpoints, the data collected for any visit after the dose escalation visit will be considered as missing.
- For time to loss of remission, the subject will be considered as having an event at the visit with a dose escalation if the event criteria are met or having a censor time at the visit with a dose escalation if the event criteria are not met.

For continuous endpoints that are measured repeatedly over time, the missing values will be handled in a linear mixed-effects model where the *mechanism of missingness* is assumed to be missing at random.

Regimen comparison between flexible dosing and fixed dosing

For the first secondary objective, analyses will be performed based on the FAS for comparisons of the following two dose regimens:

- Tofacitinib fixed 10 mg BID Dose Regimen: subjects who are initially assigned to tofacitinib 10 mg BID at randomization and stay on tofacitinib 10 mg BID until completion or discontinuation.
- Tofacitinib flexible 5 mg/10 mg BID Dose Regimen: subjects who are initially assigned to tofacitinib 5 mg BID at randomization, staying on tofacitinib 5 mg BID or having dose escalation from tofacitinib 5 mg BID to 10 mg BID.

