9.3. Analysis of Biomarker Endpoints

Fecal calprotectin and hs-CRP data and change from baseline will be summarized descriptively by dose group and by dose regimen. Fecal calprotectin and hs-CRP data will also be log-transformed (natural logarithm) for the analyses. The change from baseline will be analyzed using a linear mixed effects model with baseline value, dose group, the endoscopic subscore at baseline (0 versus 1), visit, and dose group by visit interaction all as fixed effects, and subject as a random effect.

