2.0 11 Mar 2020	2 19 Jun 2019	Revision to align with protocol amendments 1 and 2.	
 1. Section 2.1 and Section 2.2 updated to align the study objectives and study design with the protocol 2. Section 3.2 updated to including detail of censoring rule for time to loss of remission; to move biomarker endpoint to this section to align with the protocol 3. Section 3.3.1 was removed as biomarker endpoints were listed as efficacy endpoints to align with the protocol 4. Section 3.5 definition for treatment emergent adverse event has been updated based on the new standard 5. Section 5.2 added details on reporting subgroups of subjects who are initially assigned to 5 mg BID and later are retreated with 10 mg BID 6. Section 5.2.1 added p-value, method for p-value, and sensitivity analyses 7. Section 5.2.2 modified the covariance matrix used in the linear mixed effects model 8. Section 5.3.1 modified the wording since the treatment duration has been changed to month 42. 9. Section 5.3.3 was added for method of handling data after dose escalation and dose reduction. 10. Section 6.2 moved Biomarker endpoints from section 6.3.1 11. Section 6.3.1 was removed. 12. Section 6.4 added P-value with method 13. Section 6.6.1 added details to compute incidence rates. 14. Section 7.1 added additional

			information about the unblinding plan. 15. Appendix 1 updated to include visits up to Month 42, and new windowing rule for retreatment subgroup.
--	--	--	---

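### The repeated-measures model names subject as its only covariance term, so as written it pools one variance over all visits; per-visit intervals are likely too wide at the earliest visits and can be too narrow late

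*SAP*

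**What the plan says.** SAP 5.2.2 analyses change from baseline in the continuous efficacy endpoints with a linear mixed model containing baseline value, group, baseline endoscopic subscore, "visit, and dose group or regimen group by visit interaction all as fixed effects, and subject as a random effect". It states no residual covariance matrix, heterogeneous-variance option or robust standard error. Protocol 9.2.3 has the same structure ("visit, and dose group by visit interaction all as fixed effects, and subject as a random effect"), and Protocol 9.3 repeats it for log-transformed fecal calprotectin and hs-CRP.

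Estimates and 95% intervals for the "overall difference between the two dose groups or two regimen groups will be computed at each visit".

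There is one exception. For total Mayo at Month 6 under the primary objective, "the change from baseline will be analyzed using an analysis of covariance (ANCOVA) model with dose group" and baseline endoscopic subscore as factors.

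Entry is restricted. Protocol 4.1 requires a partial Mayo score of at most 2 with no rectal bleeding over the six months before baseline, and adds: "All available assessments based on Mayo score during this period must show remission". After entry, partial Mayo can range from 0 to 9 (Protocol 7.2.2) and total Mayo from 0 to 12 (Protocol 7.2.3).

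**The concern.** A random subject intercept with independent, equal-variance residuals is compound symmetry: two covariance parameters for up to 15 post-baseline visits. Every per-visit interval then uses a variance averaged over visits. That average is a poor description if subjects start in a narrow band and some later flare.

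Two things are at stake. The first is the calibration of the per-visit intervals, which are the reported output. The regimen comparison (first secondary objective) is the more exposed, because SAP 5.2 and 5.3.3 keep its data after dose escalation. The second is that SAP 5.3.1 relies on missing at random. Under that assumption a likelihood model with the wrong covariance can also bias the estimated means when data are incomplete.

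**Working it through.** **The plan's own precision figure.** Protocol 9.1 gives a half width of about 16% for the Month 6 remission difference, with 65 per group and remission above 70%. 1.96 × √(2 × 0.70 × 0.30 / 65) = 0.1575, so it reproduces (unstratified Newcombe: 15.5%). It does not depend on the mixed model. The documents give no precision figure for the continuous endpoints.

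**Inputs.** From the documents: 15 post-baseline visits for partial Mayo (its subscores are also collected at endoscopy visits), four for total and modified Mayo (Months 6, 18, 30, 42), and baseline partial Mayo between 0 and 2, so a baseline SD of at most 1. The SDs by visit, flare rates and dropout rates are assumptions, because the documents give none.

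**Formula (complete data).** The model gives every visit the average variance V̄, whereas the true variance at visit t is V_t. The interval-width ratio is √(V̄/V_t), and coverage = 2Φ(1.96 × √(V̄/V_t)) − 1. Sample size cancels.

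**Assumed SD, linear from Month 1 to Month 42, 15 visits:**

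| SD path | Width ratio M1 / M42 | Coverage M1 / M42 |
|---|---|---|
| 1.0 flat | 1.00 / 1.00 | 95.0% / 95.0% |
| 1.0 to 1.25 | 1.13 / 0.90 | 97.3% / 92.2% |
| 1.0 to 1.5 | 1.25 / 0.84 | 98.6% / 89.9% |
| 0.8 to 1.5 | 1.45 / 0.78 | 99.6% / 87.2% |
| 0.7 to 2.0 | 2.00 / 0.70 | >99.9% / 82.9% |
| 1.3 falling to 1.0 | 0.89 / 1.16 | 91.9% / 97.7% |

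The last two rows are extremes. In a simulation of complete data (65 per arm, 4,000 runs, five of these or similar paths), an unstructured covariance gave about 94-96% at every visit.

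**Assumed relapse mixture.** Let change have mean 0 and SD 0.7 in remission, and mean 4 and SD 1.5 in relapse, with relapse prevalence p. Then V = 0.49(1 − p) + 2.25p + 16p(1 − p).

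- Month 1, p = 2%: V = 0.839.
- Month 42, p = 15%: V = 2.794. With p rising linearly, V̄ = 1.837 and √(1.837/2.794) = 0.811, so coverage is 88.8%. At Month 1 it is 99.6%.
- Final p of 25% or 35%: 88.1% and 88.2% at Month 42.
- Four endoscopy visits only: about 90% at Month 42.
- p rising to its final value and then flat: at Month 42 about 94% (flat from Month 6), 93% (Month 12) and 92-93% (Month 18). With four visits and a plateau by Month 6, coverage is 95% throughout.
- Months 1, 3 and 6 only, which is all the efficacy data in the Month 6 primary analysis (SAP 7.1): Month 1 coverage falls to about 96-98%. The figures above 99% therefore apply only to the final analysis.

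**Simulated 0-9 scores with the plan's data rules** (random-intercept REML fits, 600 runs each, assumed flare and dropout rates; Monte Carlo error about 1 percentage point):

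| Scenario | Model SE / empirical SE, M1 | M42 | M42 coverage |
|---|---|---|---|
| Flares persist, all data kept | 2.62 | 0.80 | 87% |
| 5 mg data missing after escalation | 1.96 | 0.86 | 91% |
| As above, plus withdrawal after flare | 1.38 | 0.87 | 91% |
| Regimen comparison, with withdrawal | 1.52 | 0.78 | 89% |
| Dose comparison, higher equal flare rate, withdrawal | 1.51 | 0.98 | 94% |

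Month 1 intervals were too wide in every scenario; late intervals were not always too narrow. In the regimen row the raw SD was already flat or falling after Month 3 (1.54 to 1.36), so rising spread alone does not explain that shortfall. These runs do not separate the contributions of the single correlation and of unequal spread or dropout between arms.

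**The case against.** The strongest reply is that the text is silent rather than wrong, and that remission at entry limits only the baseline.

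- **Silence.** No residual covariance is stated, and the SAP change log records "Section 5.2.2 modified the covariance matrix used in the linear mixed effects model". The sponsor evidently considered the matter. This stands in part: constant variance is what the written model implies, not an explicit rule. A reader might take the log entry as a contradiction, but a log describes superseded text and is not an error. Nor does it tell a programmer what to fit.
- **Plateau.** A reader might infer from the entry criteria that spread must grow through Month 42. The documents do not support that. In the 5 mg dose group, continuous data after escalation are set to missing (SAP 5.3.3). Subjects starting other UC treatment are withdrawn (Protocol 6.4), and re-treated subjects may recover. For total and modified Mayo, a withdrawn subject's last score fills only the next endoscopy visit (SAP 5.3.1). This stands, and it makes late undercoverage conditional. It does not remove the early excess width, and the missing-data rule does not protect the regimen comparison or subjects who flare on 10 mg BID and stay in the study.
- **Scope.** Calprotectin and hs-CRP have no entry limit and are analysed on the log scale, so the restricted-range argument does not carry over to them. This stands.
- **Consequence.** No formal hypotheses are tested (SAP 5.1), and descriptive summaries by visit would show a changing spread. This stands, and keeps the point minor.

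One might also read the Amendment 1 rationale as expecting the doses to diverge late. It says only that longer follow-up allows any such divergence to be seen.

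**Conclusion.** The point holds as a minor but worthwhile improvement. As written, the model implies equal variance and equal correlation across all visits, in subjects selected for a narrow range of scores at entry. For Mayo-based scores, the earliest per-visit intervals are likely to be too wide.

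Late intervals can be too narrow if spread keeps growing: about 88-92% coverage at Month 42 under moderate rising profiles, and about 92-94% if relapse prevalence plateaus by Months 6-18. There is no shortfall for four-visit endpoints if it plateaus by Month 6, and the pattern reverses if the SD falls. All of these rest on assumed SDs, flare rates and dropout. The stronger statement, that late intervals are too narrow as a matter of fact, is not supported.

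The binary primary endpoint (CMH-weighted difference with a Newcombe interval) and the Month 6 total Mayo ANCOVA are unaffected.

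**What to change.** In SAP 5.2.2, replace the random-subject-only model as follows.

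- **Total and modified Mayo (four visits):** unstructured within-subject covariance, with 4 × 5 / 2 = 10 parameters.
- **Partial and modified partial Mayo, calprotectin, hs-CRP (15 visits):** a heterogeneous-variance structure such as heterogeneous Toeplitz (15 variances + 14 correlations = 29 parameters), or unstructured (15 × 16 / 2 = 120 parameters) if it converges.
- **Both:** a prespecified fallback order and Kenward-Roger degrees of freedom. Use small-sample-corrected sandwich errors only with a fallback structure. They correct the standard errors, but under missing at random they do not repair bias in the means from a misspecified covariance.

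Protocol section 9 lets the SAP modify analyses other than major changes to the primary endpoint, so an SAP revision is enough. It should be settled before the final analysis, and preferably before the study team is unblinded at Month 6 (SAP 7.1), so that the structure is not chosen with knowledge of the results.

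The cost is a few sentences and procedure options, somewhat wider late-visit intervals, and the need for a convergence fallback. If spread is in fact flat, little is lost: in the flat-SD simulation both models covered at about 95%.

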5.2.3. Analyses for Categorical Efficacy Data

For categorical variables, the descriptive statistics such as proportions in each category will be reported.

5.2.4. Analyses for Time to Event Data

Kaplan-Meier estimates at the scheduled visits will be computed for time-to-event endpoint.

Kaplan-Meier plots for the time-to-event variables will be produced for dose comparison and regimen comparison.

The median time-to-event will be reported for each dose group and each regimen group. Time-to-event endpoints will be tested between dose groups or regimen groups, using a log-rank test stratified by endoscopic subscore at baseline (0 versus 1). In addition, cumulative event rates and associated CIs will be estimated from the Kaplan-Meier curves for each dose group and each regimen group. The dose or regimen comparison for the proportions of the event will be made using Wald test statistics.

5.2.5. Analysis of Safety Data

Safety data will be summarized based on observed-case data by dose group, regimen group and the subgroup of subjects who are initially assigned to tofacitinib 5 mg BID and later are retreated with tofacitinib 10 mg BID. Missing data will not be imputed.

For dose groups, data collected after the dose escalation from tofacitinib 5 mg BID to 10 mg BID will not be included in the analyses.

For regimen group, data from subjects with dose escalation from tofacitinib 5 mg BID to 10 mg BID will be treated as it is.

For tier-1 adverse events, an unconditional exact method for risk difference proposed by Chan and Zhang (1999)² will be used to compare tofacitinib 10 mg BID to 5 mg BID (dose group), and tofacitinib fixed 10 mg BID to flexible 5 mg/10 mg BID (regimen group). P-values and 95% confidence intervals will be formed. For tier-2 events, the risk difference will be presented along with its 95% confidence interval using the normal approximation for the difference in binomial proportions. For tier-3 events, the risk difference will be reported.

5.3. Methods to Manage Missing Data

5.3.1. Efficacy Endpoints

For binary efficacy endpoints derived from total Mayo score or partial Mayo score, subjects with missing scores in an analysis window will be considered as non-responders.

For continuous endpoints that are measured repeatedly over time, the missing values will be handled in a linear mixed effects model where missing values are assumed to be missing at random.

For continuous endpoints based on total Mayo score and modified Mayo score, data collected after baseline to Month 6 will be considered as Month 6 if a subject has missing data at Month 6; data collected after Month 6 to Month 18 will be considered as Month 18 if a subject has missing data at Month 18; data collected after Month 18 to Month 30 will be considered as Month 30 if a subject has missing data at Month 30; data collected after Month 30 to Month 42 will be considered as Month 42 if a subject has missing data at Month 42. The description of the handling of missing data within individual components of the Mayo score is described in an [Appendix 2.1](#).

Subjects who drop out or complete the study without meeting the flare criteria will be censored at the last visit with Mayo score assessment for endpoint of time to loss of remission (flare).

Descriptive summary will also be presented based on observed data for efficacy data.

For the subgroup of subjects who are initially assigned to tofacitinib 5 mg BID and later are retreated with tofacitinib 10 mg BID, missing data will not be imputed.

For fecal calprotectin and hs-CRP, the missing values will be handled in a linear mixed effects model where missing values are assumed to be missing at random.

In addition, for hs-CRP, assayed values below the limit of quantification (BLQ) will be set to 10% less than the given assay lower limit for the specific biomarker. In listings BLQ values will be reported as “<LLQ” where LLQ will be replaced with the value for the lower limits of quantification. Assay values will be set to missing if a value has been collected as ND (ie, not done) or NS (ie, no sample).

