5.10. Rescue Medication

If a subject requires initiation of a new therapy or re-initiation of a therapy for UC, other than oral 5-ASA or sulfasalazine, the subject should be withdrawn from the study and appropriate agents should be given at the discretion of the investigator.

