6.4. Subject Withdrawal

Should a subject withdraw from active treatment, the subject should complete the procedures listed at the Month 42/ET Visit. After completing the procedures for the ET visit, the subject should return for a safety evaluation to occur approximately 4 weeks after discontinuing investigational product as per the follow-up visit (see [Section 6.2.9](#)).

Subjects will be withdrawn from the study if any of the following occurs during the study treatment period:

- If rescue therapy is initiated or re-initiated for UC with the exception of oral 5-ASA or sulfasalazine.
- If a subject undergoes surgery for UC.

A subject may be withdrawn from the study for any of the safety concerns as listed in [Appendix 4](#).

If venous thromboembolism is confirmed, discontinue treatment with tofacitinib and withdraw the subject from the study ([Appendix 4](#)).

Subjects who develop a serious infection during the study, defined as any infection (viral, bacterial, and fungal) requiring hospitalization or parenteral antimicrobials or being classified as a serious adverse event should be withdrawn from the study (see [Section 7.3.4](#)).

All abnormal laboratory events of clinical significance should be followed until the laboratory values have returned to normal or baseline levels (see [Appendix 4](#)). Subjects who meet the discontinuation criteria described in [Appendix 4](#) will be withdrawn from the study.

Subjects who are withdrawn from this study will not be permitted to return to Study A3921139.

Withdrawal of consent:

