Analysis methods are the same as the ones described above for comparison between dose groups except that data from subjects with dose escalation back to tofacitinib 10 mg BID will be treated as it is. Only the visits with missing data will be treated as non-responders.

For the second secondary objective, summary descriptive statistics will be reported for the sub-group of subjects who are initially assigned to tofacitinib 5 mg BID and later are retreated with tofacitinib 10 mg BID. Missing data will not be imputed.

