5.2. General Methods

For the primary objective, analyses will be performed for comparisons of the following two dose groups:

- Tofacitinib 10 mg BID dose group: subjects who are initially assigned to tofacitinib 10 mg BID at randomization
- Tofacitinib 5 mg BID dose group: subjects who are initially assigned to tofacitinib 5 mg BID at randomization, regardless of whether the dose is escalated back to tofacitinib 10 mg BID or not (Data collected after the dose escalation from tofacitinib 5 mg BID to 10 mg BID will not be included in the analyses.)

For the first secondary objective, analyses will be performed for comparisons of the following two regimen groups:

- Tofacitinib 10 mg BID regimen group: subjects who are initially assigned to tofacitinib 10 mg BID at randomization.
- Tofacitinib 5 mg BID regimen group: subjects who are initially assigned to tofacitinib 5 mg BID at randomization, staying on tofacitinib 5 mg BID or having dose escalation from tofacitinib 5 mg BID to 10 mg BID. Data collected after the dose escalation will be included in the analyses.

For the second secondary objective, summary descriptive statistics will be reported for the subgroup of subjects who are initially assigned to tofacitinib 5 mg BID and later are re-treated with tofacitinib 10 mg BID based on the observed case data using the original windowing rules. In addition, the efficacy data after the dose escalation will be summarized using the new windowing rule by resetting the baseline (Day 0) at the dose escalation time.

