5.2.1. Analyses for Binary Efficacy Data

The number and proportion of responders will be presented by dose group, regimen group and the subgroup of subjects who are initially assigned to tofacitinib 5 mg BID and later are retreated with tofacitinib 10 mg BID as described in [Section 5.2](#).

For dose comparison between tofacitinib 10 mg BID and 5 mg BID, the stratified estimation of the treatment difference between tofacitinib 10 mg BID and 5 mg BID in the proportion of subjects will be presented along with its 95% confidence interval (CI) with the endoscopic

subscore at baseline (0 versus 1) as the stratification factor. The Cochran Mantel Haenszel (CMH) weight method will be used for the stratified estimation of the treatment difference. The stratified CI will be constructed using the NewCombe method by Yan and Su (2010).¹ In addition, p-value based on CMH Chi-square test stratified by endoscopic subscore at baseline (0 versus 1) will be presented. The same analysis method will be used for regimen groups.

For the second secondary objective, in the subgroup of subjects who are initially assigned to tofacitinib 5 mg BID and later are retreated with tofacitinib 10 mg BID, the number and proportion of responders will be also presented overall and by the endoscopic subscore at baseline (0 versus 1).

As sensitivity analyses for handling of missing data, remission based on modified Mayo score and remission based on total Mayo score will also be analyzed using a generalized linear mixed-effects model with a logit link and with dose group, visit, dose group by visit interaction, endoscopic subscore at baseline (0 versus 1) all as fixed effects, and subject as a random effect based on data collected at Month 6, Month 18, Month 30 and Month 42 if sufficient data are available at Month 42. The estimated mean, mean difference, with p-values and 95% confidence interval based on the model will be presented at each time point for dose group and regimen group.

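### Responder rates after re-treatment with 10 mg BID use observed cases only, so subjects withdrawn for new UC therapy or UC surgery leave the denominator of later rates

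*SAP*

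**What the plan says.** **Basis of the summary.** Protocol 9.2.3 gives descriptive statistics for the re-treated subgroup and adds "Missing data will not be imputed". SAP 5.2 summarises the subjects "re-treated with tofacitinib 10 mg BID based on the observed case data using the original windowing rules". It adds a second display, in which "the efficacy data after the dose escalation will be summarized using the new windowing rule", with time restarted at escalation. SAP 5.3.1 repeats the rule: for subjects "retreated with tofacitinib 10 mg BID, missing data will not be imputed".

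**Output.** SAP 5.2.1 states that for those "retreated with tofacitinib 10 mg BID, the number and proportion of responders will be also presented overall" and by baseline endoscopic subscore.

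**Contrast.** SAP 5.3.1 opens with the general rule that a missing score in a window makes the subject a non-responder for binary endpoints. For the regimen comparison, Protocol 9.2.3 says "Only the visits with missing data will be treated as non-responders".

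**Withdrawal.** When a UC therapy other than oral 5-ASA or sulfasalazine has to be started or restarted, "the subject should be withdrawn from the study and appropriate agents should be given at the discretion of the investigator" (Protocol 5.10). Protocol 6.4 lists among the withdrawal reasons "If rescue therapy is initiated or re-initiated for UC with the exception of oral 5-ASA or sulfasalazine", and also surgery for UC; Appendix 4 repeats both. A withdrawn subject has the Month 42/ET procedures, which include endoscopy and the Mayo score, and then a 4-week follow-up visit whose procedure list (Protocol 6.3) has no Mayo score.

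**The concern.** The protocol takes out of the study the re-treated subjects who most clearly failed: those who needed another UC treatment or an operation. Once they are out, an observed-case proportion no longer contains them. A later rate then describes those still in the study and assessed, and may be read as the durability of response in everyone who was re-treated.

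The SAP does not write out the denominator. Observed-case data without imputation, set against the general non-responder rule, leaves subjects observed in the window as the natural reading.

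At stake is a named secondary objective. In the text that is not redacted, these displays (overall and by baseline endoscopic subscore) are the only response rates for re-treated subjects by themselves. The planned output shows the number and proportion of responders, but not how many subjects were due at each visit or why the others are missing. A reader of the tables could not tell whether later rates run high or low.

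**Working it through.** The plan gives no figure for this subgroup: no expected size, withdrawal share or response rate. The precision figure in Protocol 9.1 concerns the Month 6 comparison and supplies no input here. All shares below are assumptions.

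**1. Where a withdrawn failure is counted.** Scheduled endoscopy is at Months 6, 18, 30 and 42/ET (Protocol 7.2.3). In the study-day windows of SAP Appendix 1, Month 18 ends at Day 585 and Month 30 starts at Day 856. An ET score on Days 586-855 (855 - 586 + 1 = 270 days) falls in the Month 21, 24 or 27 window, where no endoscopy is scheduled, and never enters the Month 30 rate. The SAP 5.3.1 rule that moves earlier scores to Month 30 is for continuous endpoints. The first re-based window is wide (Days 2-135) and can hold an ET score, so early recapture is less exposed than later rates.

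**2. Effect on a later rate.** Let p be the response rate in all subjects due, and w_f and w_r the shares of subjects due who are missing as failures and as responders.

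- Observed rate = (p - w_r) / (1 - w_f - w_r).
- It exceeds p only if w_f/(1 - p) > w_r/p, that is, if failures leave proportionally more often than responders.
- With w_r = 0 the ratio to p is 1/(1 - w_f): 1.11, 1.25 and 1.43 for w_f of 10%, 20% and 30%.

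Assumed case: 20 subjects due, 10 true responders (50%).

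| Failures lost | Responders lost | Observed rate |
|---|---|---|
| 2 | 0 | 10/18 = 56% |
| 4 | 0 | 10/16 = 63% |
| 6 | 0 | 10/14 = 71% |
| 4 | 1 | 9/15 = 60% |
| 4 | 2 | 8/14 = 57% |
| 4 | 4 | 6/12 = 50% |
| 2 | 4 | 6/14 = 43% |

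**3. Why the number due must be derived for each subject.** Re-based day = study day - escalation day + 1, using target days.

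- Escalation on Day 270: the endoscopies on Days 540 and 900 become re-based Days 271 and 631. Day 1260 becomes Day 991, past the last re-based window (ends Day 765). Two windows hold a scheduled endoscopy.
- Escalation on Day 150: Days 180, 540 and 900 become Days 31, 391 and 751. Three windows do.
- Escalation on Day 900: Day 1260 becomes Day 361. One window does.
- Escalation on Day 586: the last scheduled visit becomes 1260 - 586 + 1 = 675, below the start of the re-based Month 24 window (Day 676). No scheduled visit is due there.

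**4. Why counting every missing value as failure would overcorrect.** Under Protocol Appendix 9 a remote visit yields the partial Mayo components but no endoscopy. Assume 20 due: 6 observed responders, 6 observed non-responders, 4 failures withdrawn earlier, and 4 continuing subjects in remission without endoscopy. Counting all missing as failure gives 6/20 = 30%, against a true 10/20 = 50%. Showing 6 responders, 10 non-responders and 4 not assessed for other reasons gives the range 30% to 50%.

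**The case against.** The strongest reply is that this is a deliberate choice, made alike in protocol and SAP, for a non-randomised, single-arm, descriptive summary in a trial that tests no formal hypotheses (SAP 5.1). The regimen comparison already counts missing visits as non-response. Number and proportion together reveal the observed denominator, and all observations are listed. No bias has been demonstrated.

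Much of this stands, and it limits the weight of the point. It does not remove it. The regimen comparison covers the whole flexible arm and gives no rate for re-treated subjects. The observed denominator does not show how many were due. Protocol 6.4 keeps in follow-up subjects who ask to stop treatment, but it withdraws from the study those who start rescue therapy.

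Four stronger readings are tempting, and the documents do not support them:

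- **Later rates must be overstated.** Appendix 4 also withdraws subjects for safety reasons, which can remove responders, so the direction is conditional.
- **All failures disappear.** Non-response alone is not a listed withdrawal reason in Protocol 6.4 or Appendix 4. Some failures stay and are observed as non-responders, and a withdrawn failure can still count once through the ET score.
- **The main comparisons are affected.** They are not; both have their own non-responder rule.
- **No other re-treatment rate is planned.** Parts of the SAP are redacted, so this can be said only of the visible text.

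**Conclusion.** The point holds in a limited form. For re-treated subjects the plan departs from its own non-responder rule, and protocol-defined failures leave the denominator of later response rates after at most one ET score. Whether those rates come out high or low depends on whether failures or responders leave proportionally more often, and the planned display does not let a reader judge this.

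The size cannot be derived from the documents. In the assumed cases with a true rate of 50%, the observed rate ranges from 43% to 71%. These figures rest on the observed-subject denominator and on invented loss shares; they are not a forecast. Because the analysis is descriptive, the change is worth making but is not essential to the trial's main conclusions.

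**What to change.** Change SAP 5.2, 5.2.1 and 5.3.1. Keep the observed-case summary and add beside it, for binary endpoints after escalation, a version built as follows:

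- **Denominator:** re-treated subjects who, given their escalation date and the visit schedule to Month 42, were due a scheduled assessment of that endpoint at that visit. For endoscopic endpoints this means study Months 6, 18, 30 and 42; for partial Mayo endpoints, every scheduled visit.
- **Non-responders:** those observed as such, plus, at all later due visits, those withdrawn earlier for new UC therapy, UC surgery or worsening UC, including worsening recorded as an adverse event. The last clause is needed because Protocol 8.2.1 counts worsening of the underlying disease as an adverse event, and Protocol 1.2 reports it as the most frequent adverse event leading to discontinuation in the maintenance study.
- **Separate line:** those not assessed for other reasons, such as withdrawal for safety reasons other than worsening UC, or a remote visit without endoscopy.
- **Shown at each visit:** number due, number assessed, and reasons for missing data.

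Cost: SAP wording, some table rows and a little programming. No new data are needed. Protocol Section 9 asks for an amendment only for major changes to the primary endpoint or its analysis. The re-treatment rate may look less favourable. The sponsor's team is unblinded from the Month 6 analysis onward (SAP 7.1), and all subjects had completed Month 6 when this SAP was finalised (SAP 5.3.3). The rule should therefore be labelled as added after that point and should use recorded withdrawal reasons only.
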